### **3.5.8.3 Management of Infusion-related Adverse Events**

Refer to the Full Prescribing Information for general management of infusion-related adverse events. In addition, for this study, if a patient experiences an IR, the following procedures will be undertaken:

- an abbreviated physical examination to capture medically relevant details, including but not limited to a thorough dermatologic examination looking for erythema, hives or peri-oral or lingual edema; a chest examination for breath sounds, stridor or wheezing; and a cardiac examination with attention to irregular heart beat.
- vital signs (temperature, respiratory rate, heart rate, blood pressure) will be captured at least every 30 minutes until the resolution or stabilization of the event.
- a 12-lead ECG with rhythm strip will be obtained and analyzed for any serious IR or any IR with angina chest discomfort, chest tightness, shortness of breath, or other cardiac symptoms.
- blood samples will be obtained for measurement of tryptase (as a marker for mast cell degranulation), C3, C4, and identification of antibodies to pegloticase (IgM, IgG, IgE) or to PEG.

The Investigator may administer any medically indicated pharmacologic agent intended to relieve symptoms (caution: no other drugs can be mixed in the KRYSTEXXA infusion bag). Signs and symptoms of the event and drugs given for treatment are to be recorded in the medical record and in the CRF/eCRF.

If in the Investigator's opinion the patient is experiencing an anaphylactic reaction (symptoms of stridor, wheezing, or cardiovascular instability, especially if associated with generalized

urticaria, pruritus, flushing, or mucosal edema), treatment with KRYSTEXXA should be permanently discontinued.

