### **1.2.2 Safety Assessments in Clinical Studies of KRYSTEXXA**

The most commonly reported serious adverse reactions from the pre-marketing controlled clinical trials in patients treated with KRYSTEXXA 8 mg every 2 weeks were gout flare, IR, and anaphylaxis.

Gout flares were more frequent during the first 3 months of treatment (74% in KRYSTEXXA-treated patients vs. 51% in placebo-treated patients), and seemed to decrease over the next 3 months (41% KRYSTEXXA vs. 67% placebo). An increase in gout flares is frequently observed upon initiation of anti-hyperuremic therapy. Thus, all patients in these studies received non-steroidal anti-inflammatory drugs (NSAID) or colchicine or both for at least 7 days as gout flare prophylaxis before beginning KRYSTEXXA; patients continued on this regimen for the 6-month treatment duration.

All patients in Phase 3 clinical trials were pre-treated with an oral antihistamine (fexofenadine, 60 mg by mouth [po], the night before and morning of the infusion), i.v. corticosteroid (200 mg hydrocortisone i.v.) and acetaminophen (1000 mg po) before the infusion to prevent anaphylaxis and IRs. Nevertheless, IRs were reported in 26% of patients treated with KRYSTEXXA 8 mg every 2 weeks compared to 5% of patients treated with placebo. Manifestations of IRs included urticaria, dyspnea, chest discomfort, chest pain, erythema, and pruritus. Approximately 3% of IRs occurred with the first dose, and most (91%) occurred during the infusion rather than after it was completed.

None of the IRs which occurred in the pegloticase studies was categorized as anaphylaxis by the investigators who enrolled subjects in the Phase 2, Phase 3, or open-label extension studies. The US FDA performed a retrospective analysis of the IRs to assess for anaphylaxis, using modified National Institute of Allergy and Infectious Disease/Food Allergy and Anaphylaxis Network (NIAID/FAAN) diagnostic criteria (Sampson et al, 2006). Using their analysis, the frequency of anaphylaxis was 6.5% in all patients treated with KRYSTEXXA 8 mg every 2 week. During randomized, placebo-controlled studies, the frequency was 5% compared to none with placebo. An independent immunologist commissioned by the sponsor to review the data based strictly upon the NIAID/FAAN clinical criteria for anaphylaxis determined the overall rate in the clinical studies to be 2.4%.

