#### **3.5.8.2 Anaphylaxis**

For this study, anaphylaxis, an allergic reaction that is rapid in onset, can be serious, and may cause death, will be defined using the NIAID/FANN diagnostic clinical criteria (Sampson et al, 2006) as described in Table 1 below. This constellation of signs and symptoms will be documented in the medical record and in the designated CRF/eCRF page. All IRs, whether described as anaphylaxis or not, will be adjudicated for anaphylaxis based on the criteria below (refer to Section 3.9).

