**Table 1 NIAID/FANN Clinical Criteria for Diagnosing Anaphylaxis**

Anaphylaxis is highly likely when the following criteria are fulfilled:
Acute onset of an illness (minutes to several hours) with involvement of the skin, mucosal tissue, or both (e.g., generalized hives; pruritus or flushing; swollen lips, tongue, or uvula)
AND AT LEAST ONE OF THE FOLLOWING:
a. Respiratory compromise (e.g., dyspnea, wheeze-bronchospasm, stridor, reduced peak expiratory flow, hypoxemia)
b. Reduced blood pressure (i.e., systolic blood pressure < 90 mm Hg or greater than 30% decrease from that person's baseline) or associated symptoms of end-organ failure (e.g., hypotonia [collapse], syncope, incontinence)

NIAID/FANN: National Institute of Allergy and Infectious Disease/Food Allergy and Anaphylaxis Network

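### The permanent-stop sentence in Protocol 3.5.8.3 is not tied to Table 1 and does not name dyspnea, and no stated route returns a positive adjudication to the treating site

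*Protocol*

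**What the plan says.** **The stop sentence.** The last paragraph of Protocol 3.5.8.3 begins "If in the Investigator's opinion the patient is experiencing an anaphylactic reaction (symptoms of stridor, wheezing, or cardiovascular instability". It then adds generalized urticaria, itching, flushing or mucosal swelling as features that strengthen the suspicion, and says that KRYSTEXXA should be permanently discontinued. It makes no reference to Table 1.

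**The definition.** Sections 3.2, 3.5.8.2, 3.7.1 and 3.8.1.3 all define anaphylaxis by the NIAID/FANN criteria. Table 1 requires acute skin or mucosal involvement plus at least one of two arms. The respiratory arm reads "Respiratory compromise (e.g., dyspnea, wheeze-bronchospasm, stridor, reduced peak expiratory flow, hypoxemia"; the other is reduced blood pressure or end-organ symptoms. On recording, 3.5.8.2 says: "This constellation of signs and symptoms will be documented in the medical record and in the designated CRF/eCRF page".

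**The IR work-up.** Section 3.5.8.3 says that "vital signs (temperature, respiratory rate, heart rate, blood pressure) will be captured at least every 30 minutes". An ECG is required for serious IRs and for "any IR with angina chest discomfort, chest tightness, shortness of breath, or other cardiac symptoms".

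**Adjudication.** All IRs are adjudicated against Table 1 (3.5.8.2, 3.9). Reports go to the committee periodically (6.1.8). The committees' reports go to the Steering Committee, which advises sponsor senior management (3.10).

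**The concern.** The protocol already accepts that anaphylaxis ends treatment for good. That policy works at the bedside only if the action sentence catches the events the study calls anaphylaxis. Here the action sentence carries its own, shorter list of signs and rests on opinion. A site that follows the list could treat a Table 1 event as an ordinary IR and give the next infusion two weeks later. The committee may classify the event as anaphylaxis, yet nothing in the text says that the site learns of it.

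Experience with this drug makes the point more than theoretical. Section 1.2.2 reports for the earlier trials: "None of the IRs which occurred in the pegloticase studies was categorized as anaphylaxis by the investigators". An independent review "based strictly upon the NIAID/FAAN clinical criteria for anaphylaxis determined the overall rate in the clinical studies to be 2.4" per cent. The agency's review, with modified criteria, gave 6.5% of patients on the 2-weekly regimen. Labels and criteria have therefore diverged before. What is at stake is re-exposure of a patient after a reaction that 3.5.8.2 itself describes as potentially fatal.

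**Working it through.** No power or sample-size figure bears on this point. The check is a comparison of text and a trace of who is told what.

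**Step 1. Compare the two lists.**

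| Element | Table 1 | Stop sentence, 3.5.8.3 |
|---|---|---|
| Basis | Criteria | Investigator's opinion |
| Skin or mucosal signs | Required | Supportive only |
| Respiratory | Dyspnea, wheeze-bronchospasm, stridor, reduced peak flow, hypoxemia | Stridor, wheezing |
| Circulatory | Low blood pressure or end-organ symptoms | Cardiovascular instability |

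Respiratory examples in Table 1: 5. Named in the stop sentence: 2. Not named: 5 − 2 = 3 (dyspnea, reduced peak flow, hypoxemia). The circulatory arm is reasonably covered.

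**Step 2. Find the practical case.** The work-up asks for no oximetry or peak-flow measurement, so hypoxemia and reduced peak flow would often go unmeasured. That leaves dyspnea. It is a realistic sign: for the earlier trials 1.2.2 says "Manifestations of IRs included urticaria, dyspnea, chest discomfort, chest pain, erythema, and pruritus". That list includes neither wheeze nor stridor. In 3.5.8.3, shortness of breath appears only as a reason for an ECG, grouped with cardiac symptoms.

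**Step 3. Run one case.** Take acute urticaria with dyspnea, no wheeze or stridor, and stable blood pressure. Table 1: skin involvement yes, respiratory compromise yes, so the definition is met. Stop sentence: no named respiratory or circulatory sign is present, so the stop depends on whether the investigator thinks of Table 1.

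**Step 4. Look for a later catch.**
- *Designated CRF/eCRF page (3.5.8.2):* the signs are recorded, but no deadline relative to the next infusion is given.
- *Adjudication (3.9, 3.10, 6.1.8):* the result goes to the Steering Committee and sponsor management. No return to the site is stated, and committee review is periodic while dosing is 2-weekly.
- *Medical monitor (3.5.6):* told of discontinuations, not of patients kept on treatment.
- *SAE report (3.8.1.2, 3.8.3):* reaches the sponsor within 24 hours if the event is serious. An outpatient event that meets no seriousness criterion does not qualify, and no hold on dosing follows from a report.

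**Step 5. Test the SUA rule.** Section 1.2.2 says that all criteria-meeting cases except one, at the first dose, had a last uric acid above 6 mg/dL. Section 3.5.2.1 requires a sample before each infusion if none was analyzed since the last visit, and stops therapy after two consecutive values above 6. A patient whose value was above 6 at the event is therefore stopped by the next routine value if it is also above 6, without any extra repeat test. Four routes remain:
1. a first-dose event;
2. a sample taken but the result not back before the infusion;
3. the following sentence in 3.5.2.1, which softens the stop to advice;
4. an event with SUA at or below 6.

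On adherence, the SAP (Report Format/Structure, item 3b) plans to count patients infused after two consecutive values above 6.

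**The case against.** The strongest reply is that the definition already does the work. The stop applies when the investigator believes the reaction is anaphylactic, and the section immediately before says what anaphylaxis means in this study. On that reading the bracketed signs are a prompt, and a wider one than Table 1 in one respect, since no skin sign is needed. This largely stands: many investigators would read it so. It fails only for those who act on the list in front of them, and the text does not rule that out.

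The second reply is the SUA rule. It also largely stands, because it runs on required samples and does not depend on the repeat test that the sponsor merely suggests. The four routes in step 5 remain. A reader might add 3.5.5, which allows treatment to resume with SUA above 6 after an interruption. That section concerns gaps such as vacation or intercurrent illness, and the documents do not support reading it as leave to re-dose after an IR.

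Third, general IR management is referred to the Full Prescribing Information (3.5.8.3, 7.2.2), which may contain a further stop rule. It is not among the documents, so this can be neither confirmed nor dismissed.

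Fourth, Table 1 says that anaphylaxis is highly likely, not certain, and an automatic stop takes discretion away from the physician for patients with few alternatives. This is a fair cost. But the protocol has already chosen permanent discontinuation for anaphylaxis; the change only aligns the trigger with the study's own definition.

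**Conclusion.** The point holds as a minor patient-safety gap in wording and information flow. The stop sentence does not make Table 1 sufficient, omits dyspnea, and is not backed by any stated return of adjudication results. Re-infusion after a Table 1 event is therefore possible for an investigator who relies on the sign list. This assumes that the Full Prescribing Information adds no stricter rule.

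The only size the text supports is the count: 2 of 5 respiratory examples named, 3 not. Both lists are illustrative, so this count is not a measure of risk.

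Four stronger readings are tempting and are not supported:
- *That the protocol permits re-infusion after anaphylaxis.* It does not; 3.5.8.2 and 3.5.8.3 read together point to stopping.
- *That the anaphylaxis rate is biased.* All IRs are adjudicated whatever the site calls them, and 6.1.6 counts at most one event of each type per patient.
- *That investigators here will miss cases as in the earlier trials.* Section 1.2.2 does not say whether those investigators were given the criteria, as these are. The contrast between none and 2.4% shows that divergence can occur, not that it will.
- *That the affected patients can be counted.* At 2.4%, 1500 patients would give 1500 × 0.024 = 36 criteria-meeting events. That is not a re-infusion count: the rate predates the SUA rule, and the documents give neither the share presenting with skin signs and dyspnea alone nor the share kept on treatment.

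**What to change.** 1. Reword the last paragraph of 3.5.8.3: *permanently discontinue KRYSTEXXA if the event meets Table 1, or if the investigator otherwise considers it anaphylactic*. Keep the present signs as examples under the second limb, so that a skin sign is still not needed there.
2. Have the site complete the Table 1 items on the already designated CRF/eCRF page for every IR before the next infusion. Allow a 'not measured' entry for peak flow and oxygen saturation. This bedside check is the main safeguard, because committee review is only periodic.
3. As a back-up, add to 3.9 and 6.1.8 that a committee determination of anaphylaxis in a patient still on treatment is sent to the treating site on the day it is made, and that dosing is held on receipt.

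The cost is one reworded sentence, earlier completion of an existing page, and one notification and hold provision. No extra patients, visits or procedures are needed. The downside is that a few patients may stop who would otherwise have continued, plus a small notification workload.

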### **3.6 Efficacy Assessments**

#### **3.6.1 Serum Uric Acid Levels**

The efficacy endpoint in this study is normalization of SUA to < 6 mg/dL. Serum uric acid will be measured using a standard clinical assay performed at local laboratories. Blood will be collected several days prior to each KRYSTEXXA infusion for the determination of SUA levels (see Section 3.5.2).

#### **3.6.2 Clinical Outcomes**

##### **3.6.2.1 Number of Swollen Joints and Tender Joints**

A count of the number of swollen joints and tender joints will be performed at Baseline/Screening, at 6 months (Visit 13) and at 12 months (Visit 26) or Early Discontinuation.

##### **3.6.2.2 Gout flares**

The occurrence and duration of gout flares will be reported throughout the study. The number of gout flares will be assessed by 6-week intervals for the first 3 months, and by 3-month intervals through the end-of-study.

##### **3.6.2.3 Number of Tophi**

A count of the total number of palpable subcutaneous tophi will be performed at Baseline/Screening, at 6 months (Visit 13) and at 12 months (Visit 26) or Early Discontinuation.

### **3.7 Safety Assessments**

#### **3.7.1 Adverse Event Profile**

Safety assessments will be focused on a further evaluation of the AE profile of KRYSTEXXA. All AEs and SAEs will be monitored and recorded. Special emphasis will be placed on capturing details of events that occur during the infusion or within 1 hour after the infusion of KRYSTEXXA in order to facilitate the characterization of infusion-related reactions, including anaphylaxis. As KRYSTEXXA is a biological agent, the development of immune complex-related AEs will also be carefully scrutinized.

- IRs will be defined as any AE or cluster of AEs, not attributable to another cause, that occurs during or within 2 hours after the infusion of KRYSTEXXA. Other cases that occur outside of the 2-hour window may also be categorized as an IR as per investigator discretion.
- Anaphylaxis will be defined using the NIAID/FANN criteria (see Table 1).
- Immune complex-related AEs will be defined as any presumptive immune complex-related disorders that are confirmed by an appropriate investigation of the disease and of

complement markers (C3, C4 levels). Clinical manifestations could include skin rash, arthralgia, arthritis, and proteinuria.

The occurrence and duration of each confirmed gout flare will be captured as part of the safety assessments.

### **3.7.2    Laboratory Evaluations**

Clinical laboratory tests such as hematology and blood chemistry panels are not required as part of this protocol. However, a blood sample will be obtained at screening to evaluate G6PD (G6PD deficiency is an exclusion criterion). Blood will also be collected at Visit 1 to establish baseline values for C3, C4, and tryptase. These blood samples will be analyzed by a central laboratory.

Additional blood samples for baseline antibodies to pegloticase and PEG will be drawn and stored frozen. These samples will be tested only for patients who subsequently have an IR, suspected anaphylaxis, or suspected immune complex disease, to be compared with samples obtained at the time of the AE. These antibody analyses will be performed by the designated bioanalytical laboratory.

### **3.7.3    Vital Signs**

Vital signs will consist of pulse rate, sitting blood pressure and body temperature (taken either orally or aurally).

### **3.7.4    Physical Examination**

Physical examinations will be performed by body system at the Screening and Visit 27 or Early Discontinuation Visit. Breast, genitourinary and rectal examinations may be excluded at the discretion of the Investigator.

Significant findings prior to the administration of KRYSTEXXA must be recorded in the patient's medical record and included on the Medical History CRF/eCRF page. Significant findings that occur after administration of KRYSTEXXA which meet the definition of an AE must be recorded in the medical record and on the Adverse Events CRF/eCRF page.

### **3.7.5    Antibody Formation**

For patients experiencing an IR, suspected anaphylaxis, or suspected immune complex disease, both baseline samples and samples obtained at the time of the AE will be assessed by a designated bioanalytical laboratory for the presence of antibodies. Validated enzyme-linked immunosorbent assays (ELISAs) will be performed by the designated bioanalytical laboratory to detect antibodies directed against pegloticase (IgG, IgM and IgE) and against the PEG portion of pegloticase (pan-anti-PEG).

### **3.8 Adverse Events**

#### **3.8.1 Adverse Event Definitions**

##### **3.8.1.1 Adverse Event**

An AE is any untoward event whether or not considered related to the use of KRYSTEXXA. Any worsening (i.e. any clinically significant adverse change in frequency or intensity) of a preexisting condition which is temporally associated with the use of KRYSTEXXA is also considered an AE. Abnormal laboratory values or test results constitute AEs only if they induce clinical signs or symptoms or require therapy, and are recorded on the Adverse Events CRF/eCRF under the signs, symptoms or diagnosis associated with them.

Baseline conditions should not be considered adverse experiences; however, worsening of a pre-existing condition may be considered an AE. Changes resulting from normal growth and development which do not vary significantly in frequency or severity from expected levels are not to be considered adverse experiences. An example of this may include, but is not limited to, menopause.

The sponsor will report all AEs according to appropriate health authority (e.g., FDA) guidelines and regulations.

##### **3.8.1.2 Serious Adverse Event**

An SAE is any AE occurring that results in any of the following outcomes:

- Death
- Is life-threatening (places the patient, in the view of the Investigator, at immediate risk of death from the event as it occurred)
- Inpatient hospitalization or prolongation of existing hospitalization (hospitalization is defined as an inpatient admission, regardless of length of stay, even if hospitalized as a precautionary measure for continued observation)
- A permanent, persistent or significant disability (substantial disruption of the ability to conduct normal life functions)
- A congenital anomaly/birth defect
- Is the result of an overdose
- A medically significant event that may jeopardize the patient and may require medical or surgical intervention to prevent one of the outcomes listed in this definition

Events NOT considered to be SAEs are:

- Hospitalization for treatment, which was elective or pre-planned, for a pre-existing condition that did not worsen
- Treatment on an emergency, outpatient basis for an event NOT fulfilling any of the definitions of serious given above and NOT resulting in hospital admission

- An AE that, had it occurred in a more severe form, might have caused death

### **3.8.1.3 Adverse Event Classifications**

Safety assessments in this study include an evaluation of the frequency and severity of IRs, anaphylaxis, and immune complex-related events. For the purposes of this study, these events shall be defined as follows:

- IRs will be defined as any AE or cluster of AEs, not attributable to another cause, that occurs during or within 2 hours after the infusion of KRYSTEXXA. Other cases that occur outside of the 2-hour window may also be categorized as an IR as per investigator discretion.
- Anaphylaxis will be defined using the NIAID/FANN criteria: acute onset of an illness (minutes to several hours) with involvement of the skin, mucosal tissue, or both (e.g., generalized hives; pruritus or flushing; swollen lips, tongue, or uvula) **AND AT LEAST ONE OF THE FOLLOWING:**
  - a. Respiratory compromise (e.g., dyspnea, wheeze-bronchospasm, stridor, reduced peak expiratory flow, hypoxemia)
  - b. Reduced blood pressure (i.e., systolic blood pressure < 90 mm Hg or greater than 30% decrease from that person's baseline) or associated symptoms of end-organ failure (e.g., hypotonia [collapse], syncope, incontinence)
- Immune complex-related disorders are caused by the deposition of immune complexes in small blood vessels in the body. This can result in the onset of diverse disorders such as glomerulonephritis, skin vasculitis, or arthritis. For the purpose of this study, any presumptive diagnosis of any of these conditions will call for a clinical investigation of the disease and of complement markers (C3, C4). If both the clinical and laboratory investigations are confirmatory, the disorder will be classified as an immune complex-related AE.

